4.3.3. Sensitivity Analysis

4.3.3.1. Varying Definitions of Missed Bolus Dose

Sensitivity analysis will be performed for the primary endpoint on the sensitivity analysis set. Varying definitions of MBD will be conducted as sensitivity analyses using a mixed-effect models for repeated measures as described in Section 4.3.2. The analyses will be completed in the sensitivity analysis set.

These include:

- MBD interval definition: 2 hours prior and 2 hours after start of glucose excursion (-2, 2), and
- MBD glucose excursion: ≥80 mg/dL (>4.4 mmol/L) rise within 2 hours.

4.3.4. Supplementary Analyses

A separate table will be produced after excluding baseline BMI from the covariate. The rest of the model and analysis will remain the same as the primary endpoint analysis.

4.4. Secondary Endpoints Analysis

The following secondary endpoints will be analyzed following the MMRM model for the masked and unmasked periods, unless otherwise noted. Baseline will be an average of the average of Week 5 and average of Week 6 (Study Period 1). Change from baseline will be calculated for Week 15, Week 16, Week 17, and Week 18 (Study Period 2). All analyses will be completed in the main analysis set. Analyses will be listed in mg/dL, participants will collect and transfer data in mmol/L, and necessary conversions will be performed in the study data tabulation models (SDTMs), ADaMs, and tables, listings, and figures (TLFs).

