### 4.3. Early Discontinuation Visits

Participants discontinuing from the study prematurely, for any reason, should return to the study site.

The participant will be required to bring his/her:

- mobile device with RMA
- CGM
- Dexcom receiver
- Tempo Pen(s) currently in use
- unused Tempo Pen(s), and
- Tempo Smart Button.

Participants will return all appropriate Sponsor-provided study materials as per Sponsor instructions.

During the visit, the site personnel will:

- collect DDs
- collect AEs
- review concomitant medications/changes in medications
- confirm up-to-date participant CGM and Tempo Smart Button data was uploaded to the RMA, and
- review and discuss glucose control and insulin dosing habits (adjust the dose if appropriate) with the participant, using the Glooko HCP Portal information.

The site will also perform the following assessments:

- weight, and
- point-of-care HbA1c measurement.

In addition, following review of Glooko summary report and discussion with the participant, the site staff will administer to the participant:

- the IORW Participant **Visit 3** Questionnaire and HFS-SF Questionnaire if the Early Termination visit takes place before Visit 3,
- the IORW participant **Visit 7** Questionnaire and HFS-SF Questionnaire if if the Early Termination visit takes place after Visit 3.

For a complete list of all required activities, please refer to the SoA (Table 1.1).

Site personnel should document details regarding the reason for discontinuation, if possible (see Section 7). Study participants will transition back to their non-study insulin (if applicable) and their non-study CGM devices (if applicable).

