2.1. Multiplicity Adjustment

A p-value of \leq 0.05 will be considered statistically significant. No adjustments for multiplicity will take place.

3. Analysis Sets

For the purposes of analysis, the following analysis sets are defined:

Participant Analysis Set	Description			
Main Analysis Set	All continuous glucose monitoring (CGM) data should be included in the final analysis, but the proportion of participants who met the minimum 70% data-obtainment requirement during 14 days should be reported as part of the data completeness. Participants with ≥70% of CGM data present for a particular day will be considered complete for the day or valid CGM day. Similarly daytime and nighttime periods will be checked separately for valid CGM period. Following the guidelines of the Advanced Technologies and Treatments for Diabetes (ATTD) consensus on CGM use, only participants with at least 10 days' worth of valid CGM data out of the last 14 days (Weeks 5 and 6) in the masked application period will be considered for the main analysis set (Danne et al. 2017; Battelino et al. 2023).			
	Among these participants, only participants that satisfy the below criteria for the unmasked application period will be considered as evaluable participants and included in the main analysis set:			
	 participants with at least 20 of 28 days' worth of CGM data (Weeks 15 to 18), or participants discontinuing early that have at least 20 days' worth of CGM data in the whole unmasked application period (Weeks 7 to 18). 			
	Efficacy analyses will be carried out on the main analysis set. To allow for this clinical trial to be generalizable to the wider population and to prevent the chance of analyzing a biased set of "only adherent" participants, efficacy analyses will be repeated on the sensitivity analysis set.			
Sensitivity Analysis Set	The sensitivity analysis set includes all participants in the main analysis set, plus participants with at least 10 days' worth of CGM data in the whole masked application period (Weeks 1 to 6), and all participants with at least 20 days' worth of CGM data in the whole unmasked application period (Weeks 7 to 18).			
Safety Analysis Set	Safety analyses will be carried out on the Safety Population, which consists of all participants with at least 1 measurement in the masked application period and/or unmasked application period.			

4. Statistical Analyses

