4.4.1.1.10. Participant and Healthcare Professional Questionnaires

Each question from participant and HCP questionnaires will be summarized in a table using frequency and percentages. Participant questionnaire summaries at Visits 1 (baseline) and Visit 3 (end of Study Period 1) from Study Period 1 will be compared to summaries at Visit 7 from Study Period 2 using shift tables. HCP questionnaire summaries will compare initial to end of study. No formal statistical testing is planned.

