4.5.3. Outcome of Study IORW Participant Questionnaires

Responses from participant questionnaires from Visits 1 (baseline), Visit 3 (end of Study Period 1), and Visit 7 (end of study) will be summarized using shift tables.

4.5.4. Continuous Glucose Monitoring Curves Integrated with Data Received from the Tempo Pen/Smart Button

The MBD and mistimed bolus dose will be calculated using CGM plots and algorithm explained in Section 4.3.1.1. The association between MBD and mistimed bolus doses with TIR, TAR, TBR and HbA1c will be analyzed using the Spearman rank order correlation. This analysis will be done on the sensitivity analysis set.

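### Participant acceptability questionnaires are tied to an analysis set defined by CGM days, and the forms completed at early termination have no assigned place in the tables

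*SAP*

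**What the plan says.** **Analysis set.** SAP 4.4 opens with rules for all secondary endpoints, among them "All analyses will be completed in the main analysis set". Participant questionnaires are item 4.4.1.1.10 in that section, and no other population is named there. SAP 3 admits a participant to the main set on two conditions:

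- at least 10 valid CGM days in the 14 days of Weeks 5 and 6; and
- at least 20 of 28 CGM days in Weeks 15 to 18 or, for those who discontinue early, at least 20 CGM days anywhere in Weeks 7 to 18.

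SAP 3 and 4.1 repeat efficacy analyses on a sensitivity set, "to prevent the chance of analyzing a biased set of 'only adherent' participants". That set is defined by CGM days too, counted over the whole of each period.

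**Timepoints.** In SAP 4.4.1.1.10, the Visit 1 and Visit 3 summaries "will be compared to summaries at Visit 7 from Study Period 2 using shift tables". SAP 4.5.3 lists the same participant forms as exploratory: responses at Visits 1, 3 and 7 "will be summarized using shift tables", with no set named. Protocol 9.3.4 plans frequencies, percentages and shift tables, and also names no set.

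**Collection.** Protocol 4.3 and the Schedule of Activities also collect questionnaires at early termination. Someone leaving before Visit 3 completes the Visit 3 form. Sites give the Visit 7 "Questionnaire and HFS-SF Questionnaire if if the Early Termination visit takes place" after Visit 3. Neither document says in which table or column these forms are reported.

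**The concern.** The entry rule for the table is related to the thing being rated. CGM days count only if the sensor is worn, the receiver is kept within 6 metres (Protocol 6.1) and the data are uploaded by cable at least every 30 days (Protocol 2.4.2). A participant who finds this inconvenient or unreliable is more likely to fall short of the thresholds, and so to drop out of the table on convenience and ease of use. The questionnaire itself needs no CGM data, so the restriction gains nothing analytically.

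The early-termination forms matter because of when the scheduled ones are given. The Visit 1 form is completed before the platform is demonstrated (Protocol 4.2.2.2), and the Visit 3 form before the dosing data are unmasked (Protocol 4.2.4). For someone who leaves during Study Period 2, the form completed at termination is the only rating of the unmasked platform.

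At stake is the credibility of one descriptive secondary objective. If the denominator and the handling of leavers' forms are settled only once the data are in, the reported acceptability will depend on a choice made after the fact.

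**Working it through.** **1. Does the main-set rule reach the questionnaires?** The qualifier in SAP 4.4 (unless otherwise noted) attaches to the MMRM method, not to the population. Where the SAP wants another set it says so: 4.3.3.1 and 4.5.4 name the sensitivity set, and 6.1.1 names three sets. Silence in 4.4.1.1.10 therefore leaves the section rule in force.

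**2. Does the sensitivity-set repeat cure it?** Not fully. SAP 4.1 promises the repeat for efficacy analyses, while SAP 4.4 puts all its analyses in the main set, and nothing says whether a satisfaction form counts as efficacy. If it does, entry still requires CGM days: 10 in Weeks 1 to 6 and 20 in Weeks 7 to 18. The wording leaves open whether both are needed or either will do.

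**3. Which forms lack a column?**

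| Form collected (Protocol 4.3, Schedule of Activities) | Place in SAP 4.4.1.1.10 or 4.5.3 |
|---|---|
| Visit 1, Visit 3, Visit 7 as scheduled | named |
| Visit 3 form at termination before Visit 3 | not stated |
| Visit 7 form at termination after Visit 3 | not stated |

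Some leavers can never enter the main set. Anyone who leaves fewer than 20 days after Visit 3 cannot have 20 CGM days in Weeks 7 to 18.

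**4. How many participants could be affected?** The documents give no figure for the questionnaires, so the sample-size inputs are the only guide.

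- Check of the plan's own figure: per-period SD 0.419 and correlation 0.2 give an SD of the difference of 0.419 × √(2 × 0.8) = 0.530. A two-sided paired t-test at 0.05 for a difference of 0.323 then needs n = 24 (power 81.6%), which matches Protocol Table 9.1.
- Planned loss (Protocol 9.4, SAP 5): 0.35 × 50 = 17.5, so about 17 to 18 participants outside the main set and 32 to 33 inside.
- At the planned minimum of 24 evaluable: 50 − 24 = 26 outside.

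**5. Illustration only.** Assume 85% of 33 evaluable participants are satisfied (28.05 people). Let p be the assumed rate among the other 17, and m the number of them who have a form. The rate in all responders is (28.05 + m × p) / (33 + m).

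| | p = 30% | p = 50% | p = 70% |
|---|---|---|---|
| m = 17 (all answer) | 33.15/50 = 66% | 36.55/50 = 73% | 39.95/50 = 80% |
| m = 8 (assumed) | 30.45/41 = 74% | 32.05/41 = 78% | 33.65/41 = 82% |
| m = 0 | 85% | 85% | 85% |

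The main-set table would show 85% in every cell. Neither p nor m can be taken from the documents.

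**The case against.** The case for leaving the text alone has real substance.

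- **The sentence in SAP 4.4 is general.** It sits in a paragraph about the MMRM, the Week 5 and 6 baseline and unit conversion. Read literally it would also cover HCP questionnaires, whose respondents belong to no participant set. It may be an untailored sentence rather than a decision. That is plausible, but it remains the only population rule that applies, and an analyst following it would restrict the tables.
- **SAP 4.5.3 and Protocol 9.3.4 name no set.** This stands. It means the same forms could be tabulated in different populations under two headings, which is itself a reason to specify.
- **The SAP already guards against an adherent-only sample.** The sensitivity set softens the selection but, as shown, does not remove the CGM requirement.
- **Failing the CGM thresholds is not the same as disengagement.** This stands. The sample-size text expects some losses from technical problems, and there is no threshold on Smart Button or app use, so a poor pen user with enough CGM days stays in.
- **The termination form after Visit 3 is the Visit 7 form itself.** A programmer could table it with Visit 7. True: the SAP is silent, not prohibitive. Without a rule, though, it could equally be omitted.
- **The illustration can exaggerate.** This stands. Those leaving before Visit 3 complete a different form, those lost to follow-up may give none, and those not reaching the unmasked stage may be replaced. With 8 of 17 answering at 50%, the gap is 7 points rather than 12.
- **The endpoint is descriptive, with no formal testing.** This limits the weight of the point but does not answer it.

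**Conclusion.** The point holds as a modest, cheaply corrected weakness in a descriptive secondary endpoint. A stated rule gives the acceptability tables a denominator selected on CGM days, and the questionnaires collected at early termination have no assigned place. Acceptability may therefore be reported mainly from participants who kept wearing and uploading the CGM. Higher reported satisfaction is the likely direction, but nothing in the documents demonstrates it.

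A reader might infer three stronger things, and the documents support none of them:

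- *That only adherent participants are reported.* Early leavers who meet the Weeks 5 and 6 rule and have at least 20 unmasked CGM days are in the main set, and SAP 4.5.3 is not tied to any set.
- *That only Visit 7 is analysed.* Visits 1 and 3 are summarised as well; Visit 7 is simply the only timepoint named after unmasking.
- *That early-termination forms are excluded.* They are unassigned.

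On size, the firm statement is that the plan's 35% allowance is about 17 to 18 of 50 participants. It combines dropout with missing CGM data, and the share who would have a form is not given. Any satisfaction percentage is illustrative. HCP questionnaires, the primary analysis and the sample size are unaffected.

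**What to change.** Amend SAP 4.4.1.1.10 and 4.5.3, before results are seen, to state that:

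1. participant questionnaires are summarised in all enrolled participants with a response, regardless of CGM days;
2. the end-of-use column is Visit 7, or early termination after Visit 3, with the two sources also shown separately;
3. Visit 3 forms completed at termination before Visit 3 are handled the same way at Visit 3: combined, and also shown separately;
4. the main-set table is kept as supportive.

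Reporting the number of forms received from each source beside the number enrolled would show how far non-response still limits the result.

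**Cost.** SAP wording and one more table, using data already scheduled. The downside is that early-termination answers reflect less than 12 weeks of unmasked use, which the separate display makes visible.

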4.4.1. Secondary Endpoints

4.4.1.1. Main Analytical Approach

4.4.1.1.1. Continuous Glucose Monitoring Time In Range (≥70 to >180 mg/dL) in the Masked Versus Unmasked Portions of the Study

CGM percent of time in range (≥70 and ≤180 mg/dL) and change from baseline will be summarized descriptively by study period and by week, presented in a table. Actual values from Study Period 1 and Study Period 2 will be analyzed using an MMRM. Example SAS Software version 9.4 program code for the MMRM is as follows:

```
proc mixed data = <data>;
    Class StudyPeriod usubjid week;
    Model TIR = StudyPeriod BaseBMI BaseHbAlc week/ddfm=
kenwordroger;
    Random Usubjid / subject = usubjid;
    Repeated week/ subject = usubjid type = un rcorr;
    Lsmeans StudyPeriod/diff cl pdiff;
run;
```

4.4.1.1.2. Continuous Glucose Monitoring Time Above Range (>180 mg/dL) in the Masked Versus Unmasked Portions of the Study

CGM percent of time above range (>180 mg/dL) and change from baseline will be summarized descriptively by study period and by week, presented in a table. Actual values from Study Period 1 and Study Period 2 will be analyzed using an MMRM. The setup of the data will be the

same as in Section 4.3.2. Example SAS Software version 9.4 program code for the MMRM is as follows:

```
proc mixed data = <data>;
    Class StudyPeriod usubjid week;
    Model TAR= StudyPeriod BaseBMI BaseHbAlc week/ ddfm
=kenwordroger;
    Random Usubjid / subject = usubjid;
    Repeated week/ subject = usubjid type = un rcorr;
    Lsmeans StudyPeriod/diff cl pdiff;
run;
```

4.4.1.1.3. Continuous Glucose Monitoring Time Above Range (>250 mg/dL) in the Masked Versus Unmasked Portions of the Study

CGM percent of time above range (>250 mg/dL) and change from baseline will be summarized descriptively by study period and by week, presented in a table. Actual values from Study Period 1 and Study Period 2 will be analyzed using an MMRM. The setup of the data will be the same as in Section 4.3.2. Example SAS Software version 9.4 program code for the MMRM is as follows:

```
proc mixed data = <data>;
    Class StudyPeriod usubjid week;
    Model TAR = StudyPeriod BaseBMI BaseHbAlc week/ ddfm
=kenwordroger;
    Random Usubjid / subject = usubjid;
    Repeated week/ subject = usubjid type = un rcorr;
    Lsmeans StudyPeriod/diff cl pdiff;
run;
```

4.4.1.1.4. Continuous Glucose Monitoring Time Below Range (54 mg/dL \leq TBR \leq 70 mg/dL and < 54 mg/dL) in the Masked Versus Unmasked Portions of the Study

CGM percent of time below range (<70 mg/dL and < 54mg/dL) and change from baseline will be summarized descriptively by study period and by week, presented in a table. Actual values from Study Period 1 and Study Period 2 will be analyzed. The setup of the data will be the same as in Section 4.3.2. Example SAS Software version 9.4 program code for the MMRM is as follows:

```
proc mixed data = <data>;
    Class StudyPeriod usubjid week;
    Model TBR = StudyPeriod BaseBMI BaseHbAlc week/ ddfm
=kenwordroger;
    Random usubjid / subject = usubjid;
    Repeated week / subject = usubjid type = un rcorr
```

Lsmeans StudyPeriod/diff cl pdiff;

run;

run;

4.4.1.1.5. Coefficient of Variation and Mean Sensor Glucose from Continuous Glucose Monitoring Data

Coefficient of variation (CV) will be summarized descriptively by study period and by week, presented in a table. In addition, mean sensor glucose will be collected. Actual values and change from Study Period 1 to Study Period 2 will be analyzed using an MMRM. Example SAS Software version 9.4 program code for the MMRM is as follows:

```
proc mixed data = <data>;
     Class StudyPeriod usubjid week;
     Model CV = StudyPeriod BaseBMI BaseHbA1c week / ddfm =
     kenwordroger;
     Random usubjid / subject = usubjid;
     Repeated week / subject = usubjid type = un rcorr;
     Lsmeans StudyPeriod/diff cl pdiff;
run;
In addition, mean sensor glucose will be collected and MMRM will be generated as follows:
proc mixed data = <data>;
     Class StudyPeriod usubjid week;
     Model mean glucose = StudyPeriod BaseBMI BaseHbA1c week / ddfm =
     kenwordroger;
     Random usubjid / subject = usubjid;
     Repeated week / subject = usubjid type = un rcorr;
     Lsmeans StudyPeriod/diff cl pdiff;
```

4.4.1.1.6. Occurrence and Change in Mistimed Bolus Doses Frequency

Mistimed bolus dose is defined as administering a bolus dose from the start of a glucose excursion to 1 hour after the start of glucose excursion and before the peak of the glucose excursion. From the plot (Figure 4.1) in Section 4.3.1, if the correct or optimum time to administer a premeal insulin dose is between 1700 and 1800 hours, then an insulin dose between 1800 and 1900 hours will be considered a mistimed bolus dose. Mistimed bolus dose will be calculated and summarized in a table. The definition of a glucose excursion remains the same for an MBD and mistimed bolus dose.

Actual values and change in mistimed boluses doses will be summarized descriptively in a table for each study period and for each week as well. The average value of Weeks 5 and 6 will be used for baseline. Similar statistical analysis will be performed as MBD:

```
proc mixed data = <data>;
    Class StudyPeriod usubjid week;
    Model average_mistimed_bolus_dose = StudyPeriod BaseBMI BaseHbAlc week / ddfm = kenwordroger;
    Random usubjid / subject = usubjid;
    Repeated week / subject = usubjid type = un rcorr;
    Lsmeans StudyPeriod/diff cl pdiff;
run;
```

4.4.1.1.7. Total Insulin Dose per Day, Basal Dose, and Insulin Dose per Type of Meal

The change in insulin doses: basal and mealtime, ratio basal/mealtime, dose per meal as well and total dose in IU/kg, will be calculated and summarized descriptively in a table.

The type of meal will be defined by time intervals: breakfast (0600–1000 hours), lunch (1200–1500 hours), and dinner (1900–2200 hours).

Example SAS Software version 9.4 program code for the MMRM model is as follows:

```
proc mixed data = <data>;
    Class StudyPeriod usubjid week;
    Model Aval = StudyPeriod BaseBMI BaseHbA1c week/ ddfm = kenwordroger;
    Random usubjid / subject = usubjid;
    Repeated week/ subject = usubjid type = un rcorr;
    Lsmeans StudyPeriod/diff cl pdiff;
run;
```

